The intervention being tested is the environmental intervention, but all participants will receive asthma medication based on national guidelines. All will receive a short-acting beta agonist, albuterol, for use as a reliever medication. All participants, at least at the start of the study, will also receive a controller medication, Flovent or Advair or an equivalent alternative medication.

- b. Justification and safety information if FDA approved drugs will be administered for non-FDA approved indications or if doses or routes of administration or participant populations are changed. N/A

Justification and safety information if non-FDA approved drugs without an IND will be administered. NA

6. Study Statistics

- a. Primary outcome variable. The primary outcome variable is the treatment step that the participant is assigned at the 6 month clinic visit (see treatment algorithm above).

- b. Secondary outcome variables.

Secondary outcomes include: (1) daily inhaled corticosteroid dose, (2) allergic inflammation markers (allergen-specific IgE, FENO, (3) measures of asthma control (days of short-acting beta agonist use, days of slowed activity due to asthma, days of exercise-induced symptoms, days of cough without an upper respiratory infection, nights of waking due to asthma symptoms), and (4) measures of exacerbations (oral corticosteroid bursts, hospitalizations, emergency department visits, and unscheduled physician visits). Other secondary outcomes include FEV1/FVC, % change in FEV1 after albuterol, and asthma severity, as measured by the CASI.⁽²⁹⁾

- c. Statistical plan including sample size justification and interim data analysis.

Power Estimate

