The power estimate is based on assessment of the primary outcome, treatment step, at 6 months. In the ICAS trial, the ECS resulted in a reduction of 0.8 symptom days/2 weeks within two months of randomization.⁽¹³⁾ The authors of the paper make the point that this effect size is similar to that seen with controller medications. In PREACH, the SHS intervention trial, there was an increase of 1.9 symptom-free days/2 weeks at six months in the group receiving air purifiers compared to the control group. This effect, which was observed with air purifiers alone and no other environmental intervention, is also similar in magnitude to low dose, inhaled corticosteroids, which resulted in an increase of 2 symptom-free days/2 weeks compared to placebo among children with persistent asthma (CAMP).⁽⁹⁾ With a multi-faceted intervention as proposed for this study, we expect a significantly larger effect size than observed with air purifier deployment alone. In terms of treatment step, low dose ICS is one “step-up” from no controller medication, which reflects the difference in controller medication requirement that our proposed study is powered to detect. Further, a 1 step reduction in controller medication requirement would also be the point at which an ECS would likely be cost effective. For example, in the ICAS trial,⁽¹³⁾ the intervention, which was effective for two years, cost approximately \$1500, similar to the cost of a one year supply of low dose ICS. There will be 7 possible treatment steps (Table 6) and, based on the distribution of participants across treatment steps in other studies, we will assume a mean treatment step of 4.0 at baseline among participants in both groups and have estimated the power to detect a difference of 1 treatment step between the two groups, with a standard deviation between 1.5 and 2. With a sample size of 200, and assuming alpha=0.05, we will have a power of 0.94 to detect a difference of this magnitude. With a drop-out rate of ~12%, there will be a power of 0.90. (Table 6)

Treatment step difference	SD	Power for n=200	Power for n=175
0.75	1.5	0.94	0.90
	2.0	0.75	0.69
1.00	2.0	0.94	0.90
	2.5	0.80	0.74

Analysis Plan

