The primary outcome will be the treatment step that is assigned at the final clinic visit at six months. The six month time point has been chosen because successful ECS trials have observed an effect by six months, but an effect may not be observed before this time because it takes several months for indoor allergen levels to fall after implementing an environmental intervention. The secondary outcome will be total daily ICS dose assigned at this same visit, expressed in milligrams. The primary analysis dataset will be an intent-to-treat (ITT) dataset and will include participants with six month outcome data collected, regardless of whether they completed all of the ECS activities. A per-protocol analysis will also be performed and will be performed on the dataset of participants with six month

outcome data who completed at least one intervention visit (one IPM visit or for the Medication Group, receipt of ECS educational materials). Exploratory data analysis for both Aims 1 and 2 will include compilation of descriptive statistics to detect any outliers or discrepancies in data and to compare baseline characteristics and demographics between ECS+Medication and Medication Groups. Continuous variables will be summarized using means, medians, standard deviations, ranges, and interquartile ranges. Continuous variables will be analyzed using non-parametric approaches or will be transformed to meet assumptions of normality required for parametric statistics. Categorical variables will be tabulated. The percent of participants who complete the study, losses to follow-up, missed visits, and reasons for discontinuation will be presented.

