The primary outcome will be the participant's assigned treatment step at the six month clinic visit (as described above). Secondary outcomes include: (1) daily inhaled corticosteroid dose, (2) allergic inflammation markers (allergen-specific IgE, FENO₂), (3) measures of asthma control (days of short-acting beta agonist use, days of slowed activity due to asthma, days of exercise-induced symptoms, days of cough without an upper respiratory infection, nights of waking due to asthma symptoms), and (4) measures of exacerbations (oral corticosteroid bursts, hospitalizations, emergency department visits, and unscheduled physician visits). Other secondary outcomes include FEV₁/FVC, % change in FEV₁ after albuterol, and asthma severity, as measured by the CASI.⁽²⁹⁾ We will subtract baseline levels of the treatment step from the step assigned at the 6 month CV to assess the within-person change in treatment step over time. Differences over time in the intervention group will be compared to those in the control group using a generalized linear modeling approach and a significance cutoff of 0.05. Assessment of significance adjusting for multiple comparisons will be done using the method of Benjamini and Hochberg.⁽³⁷⁾ Regression models will be used to adjust for potential confounders and to test for interactions with potential effect modifiers. A similar analytic approach will be used for other clinical and inflammation outcomes, with appropriate statistical tests and models for the different types of outcome variable data, such a Chi-Square test and logistic regression for dichotomous outcomes.

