Potential confounders will be explored by examining any differences between the intervention and control groups and also assessing the association between the potential confounders at baseline and at the final study visit. In addition, potential confounders will be included in the models to determine the impact the variables have on the relationship between group assignment and the outcome. Some specific confounders that will be carefully examined include baseline allergen and pollutant levels, treatment step at baseline, and season. Potential effect modifiers, such as baseline pollutant and allergen levels, baseline asthma severity, baseline asthma control, baseline lung function, and number of positive skin tests, will also be examined by stratifying analyses and creating an interaction term to include in the final models. Analyses will be stratified by these potential response predictors and interaction terms will be included in models to determine if any of these factors predict responsiveness to the intervention.

To measure the change in home airborne particulate matter (PM_{2.5} and PM_{2.5-10}) and indoor allergen concentrations (cat, dog, mouse, cockroach, and dust mite) among study participants. Distributional properties of baseline levels of pollutants (PM_{2.5} and PM_{2.5-10}) and allergens will be assessed using histograms and boxplots and any necessary transformations to these variables will be conducted to obtain approximately Normal distributions. We will subtract baseline levels of these exposures from levels recorded 6 months post-randomization to assess the within-person change in exposure over time. Differences over time in the intervention group will be compared to those in the control group via standard *t*-tests using a significance cutoff of 0.05. Assessment of significance adjusting for multiple comparisons will be done using the method of Benjamini and Hochberg.

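### The one comparison tested at 0.05 is change in treatment step with no covariates named; baseline step is neither a fixed covariate nor tied to a visit

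*Combined protocol and SAP*

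**What the plan says.** Section 6.a of the combined protocol and SAP defines the endpoint as a final value: "The primary outcome variable is the treatment step that the participant is assigned at the 6 month clinic visit". The Power Estimate in section 6.c rests on the same quantity: "The power estimate is based on assessment of the primary outcome, treatment step, at 6 months". It adds "we will assume a mean treatment step of 4.0 at baseline among participants in both groups", without naming the visit.

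The Analysis Plan in section 6.c then moves to change: "We will subtract baseline levels of the treatment step from the step assigned at the 6 month CV". It goes on: "Differences over time in the intervention group will be compared to those in the control group using a generalized linear modeling approach", with significance at 0.05. No covariates are named for this comparison, so it reads as unadjusted.

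Regression models that adjust for confounders follow in a separate sentence. The next paragraph says that "potential confounders will be included in the models to determine the impact the variables have on the relationship between group assignment and the outcome", and lists treatment step at baseline with allergen and pollutant levels and season as factors to be looked at carefully. No sentence says which result, adjusted or unadjusted, is the primary one. The approach is carried over to the secondary endpoints: "A similar analytic approach will be used for other clinical and inflammation outcomes".

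Under Study Procedures 3.a, the treatment algorithm is applied at screening and again at CV1. CV1 is month 0 in the visit schedule and the visit of randomisation. The first ECS module is delivered after CV1.

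**The concern.** There are two linked gaps.

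The first is precision. In a randomised trial with a pre-randomisation value of the outcome, subtracting that value fixes its coefficient at 1. Using it as a covariate lets the data set the coefficient, and in a linear model the large-sample variance is never larger. The step is already recorded before any intervention, so the gain is nearly free.

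The second is that the plan admits more than one primary result. Unadjusted change and baseline-adjusted step estimate the same arm difference under randomisation, but in a given dataset their estimates, intervals and p-values differ. The undefined baseline adds to this, because the screening and CV1 steps can differ for the same child and give different changes. This is the trial's single primary test, and the Background and Benefits sections say its result is meant to inform payer policy and practice guidelines. The test should be identifiable before the data are seen.

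**Working it through.** **1. The plan's own figures.** Inputs from the Power Estimate: two arms 1:1, alpha 0.05, n=200 or 175, and the tabulated differences and SDs. Method: two-sided, two-sample noncentral t.

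| Difference | SD | n=200: stated / computed | n=175: stated / computed |
|---|---|---|---|
| 0.75 | 1.5 | 0.94 / 0.940 | 0.90 / 0.908 |
| 0.75 | 2.0 | 0.75 / 0.751 | 0.69 / 0.694 |
| 1.00 | 2.0 | 0.94 / 0.940 | 0.90 / 0.908 |
| 1.00 | 2.5 | 0.80 / 0.804 | 0.74 / 0.749 |

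The table reproduces to within 0.01. It matches an unadjusted two-sample comparison in which no baseline correlation enters.

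**2. Change against adjusted.** Let SD be the same at both visits and r the baseline-to-6-month correlation. Then SD of change = SD × √(2(1−r)), and residual SD after adjustment = SD × √(1−r²). The variance ratio is 2(1−r)/(1−r²) = 2/(1+r). The documents do not give r, so a range is shown. Taking SD 2 as the SD of the 6-month step is also an assumption: the Power Estimate implies it but does not say so. For a 1-step difference at n=175:

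| r | SD of change | Adjusted SD | Variance ratio | Power, change | Power, adjusted |
|---|---|---|---|---|---|
| 0.3 | 2.37 | 1.91 | 1.54 | 0.79 | 0.93 |
| 0.5 | 2.00 | 1.73 | 1.33 | 0.91 | 0.97 |
| 0.7 | 1.55 | 1.43 | 1.18 | 0.99 | 1.00 |

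**3. When the gain is small.** If the SD of change is 1.5, unadjusted change at n=175 already has power 0.992 for 1 step. Adjustment can then add at most 1 − 0.992 = 0.008, under one percentage point. An illustrative simulation of the protocol's step rules (32 scenarios, all inputs assumed, steroid branch and physician override ignored) gave SDs of change no larger than 1.52. At 1.52, power for change is 0.991 for 1 step and 0.901 for 0.75 step. With the step in force on arrival at CV1 as baseline, the variance ratio ranged from 1.00 to 1.37, median 1.12.

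**4. How far the two results can part.** At n=175 and SD 2, the standard error of the baseline mean difference is 2 × √(1/88 + 1/87) = 0.30. A chance baseline difference of 0.5 step shifts the unadjusted change estimate by −(1−r) × 0.5: −0.35, −0.25 or −0.15 step at r = 0.3, 0.5 or 0.7. The adjusted estimate is not shifted. In five of the simulated scenarios with no true effect, the two tests disagreed at 0.05 in 0.9–3.7% of trials. Reporting the more favourable of the two would give a false-positive rate of 5.5–6.8%.

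**5. Which baseline.** Take a child who arrives at screening on Step 3 with control level 4; the screening table assigns Step 5. At CV1, with control level 1 and adherence of at least 50%, the rule for CVs 1–4 lowers this to Step 4. The candidate baselines are 3 (arrival at screening), 5 (in force on arrival at CV1) and 4 (assigned at CV1). A 6-month step of 4 is then a change of 4−3 = +1, 4−5 = −1 or 4−4 = 0.

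**The case against.** The strongest reply is that the plan does state a comparison. The 0.05 cutoff is attached to one contrast, between-arm change in step, and the adjusted models come afterwards, so the natural reading is unadjusted change first and adjusted models as support. That reading is fair. A reader might infer that no primary analysis exists at all, and the text does not support that. What stands is that the plan never says this is the order, and that unadjusted change is not the most precise use of data already collected.

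A reader might also infer that the primary test is open to transformation or rank methods, from "Continuous variables will be analyzed using non-parametric approaches or will be transformed to meet assumptions of normality required for parametric statistics". That sentence sits with the exploratory and descriptive text and concerns continuous variables. The step is a seven-level score with its own analysis sentences, so this is not good evidence of further freedom in the primary test.

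It can be said that adjustment buys little. If the SD of change is near 1.5, that is correct for a 1-step effect. The larger gains at r=0.3 and 0.5 need SDs of change of 2.37 and 2.00, above anything in the simulation. Since its inputs are all assumed, it cannot exclude those values, but they should be read as the unfavourable end of a range.

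Finally, CV1 is labelled month 0 and is the randomisation visit, so it is the obvious baseline. That stands, but it does not choose between the step in force on arrival and the step newly assigned there. Linear regression on a bounded seven-level score is one defensible choice among several. In the five null scenarios its type I error was 0.045–0.054, which is adequate.

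**Conclusion.** The point holds as a matter of precision and of naming one primary result. The size depends on r, which the documents do not give. Power for 1 step at n=175 rises from 0.79 to 0.93 at r=0.3, from 0.91 to 0.97 at r=0.5, and by less than one percentage point once the SD of change is about 1.5 or less. These figures assume equal variances at the two visits and that the tabulated SD of 2 is that of the 6-month step.

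Three stronger conclusions are tempting and are not supported. The change comparison is not shown to be biased: under randomisation it has the same expected arm difference as the adjusted analysis. That equality applies to the full randomised set; the restriction to children with 6-month data is a separate matter that neither analysis settles. The power table is not in error. And the trial is not shown to be underpowered: when the SD of change is about 1.5 or less, the stated power is met with or without adjustment.

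**What to change.** State one primary analysis in section 6.c: linear regression of the step assigned at 6 months on arm, with baseline step as a required covariate. The arm estimate is then the same whether the outcome is entered as the step or as its change, which reconciles the endpoint in section 6.a with the comparison in the Analysis Plan.

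Define baseline step as the step in force on arrival at CV1. It is fixed before randomisation, so the order of step assignment and randomisation within CV1 does not matter.

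Label unadjusted change, and models with further confounders, as supportive. Use the same baseline-adjusted form for continuous secondary outcomes measured at baseline, and name the baseline visit for each. For serum IgE that visit is screening, because the schedule has venipuncture only at screening and CV4.

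The cost is SAP wording and one degree of freedom. No new data are needed, no treatment rule is touched, and within-person change can still be reported.

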Questionnaires: Questionnaires that capture medication use, asthma symptoms, asthma-related health care utilization will be administered at all clinic visits. The questionnaires are based on questionnaires used in urban populations and

will capture symptoms over a two week period of time, and medication use over a two week period of time as well as asthma control as assessed by the validated Asthma Control Test.^(27, 28) Asthma severity will be assessed by the validated Composite Asthma Severity Index (CASI).⁽²⁹⁾ Asthma control will be assessed at CV1-4 slightly different from the screening visit. (See assessment Tables 2 and 2a).

Table 2. Assessment of Control Level at CV0				
	Days of asthma symptoms or rescue medication use/previous 2 weeks	Nights of waking with asthma symptoms or for rescue medication use/previous 2 weeks	FEV ₁ percent predicted	Steroid bursts, previous six months
Control Level 1	0-3	0-1	≥85%	0
Control Level 2	4-9	2	80-<85	1
Control Level 3	10-13	3-4	70-<80	2
Control Level 4	>13	5-14	<70	>2

Table 2a. Assessment of Control Level at CV1-4				
	Days of asthma symptoms or rescue medication use/previous 2 weeks	Nights of waking with asthma symptoms or for rescue medication use/previous 2 weeks	FEV ₁ percent of best (the best FEV ₁ they've had since starting the study)	Steroid bursts, since last visit
Control Level 1	0-3	0-1	>85%	NO
Control Level 2	4-9	2	80-<85	YES
Control Level 3	10-13	3-4	70-<80	-
Control Level 4	>13	5-14	<70	-

Because school age children and adolescents will be enrolled, we will administer the questionnaires to the primary caregiver of children 5-11 years, and to both the study participant and his/her caregiver for adolescent study participants, age 12-17. The questionnaires will be modified accordingly. Although previous studies have indicated concordance between the adolescent's and the caregiver's

responses,⁽³⁰⁾ we will collect data from both so that we have the ability to assess the concordance rate within our study population.

Urine collection: Urine will be collected for pregnancy testing in females of childbearing capacity. Urinary cotinine will be assessed by a rapid detection method to exclude active smokers in children 12 and older. In children 12 and older, a NicAlert value of 4 or greater will exclude them from eligibility for randomization. Urine will also be stored for later analysis of cotinine in all children to assess second hand smoke exposure.

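### Section 6c gives exacerbations no counting window, count model or role for CV2–CV3 data, and its month-6-minus-baseline approach fits the secondary outcomes poorly

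*Combined protocol and SAP*

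**What the plan says.** For the primary outcome, the Analysis Plan in section 6c states: "We will subtract baseline levels of the treatment step from the step assigned at the 6 month CV". The arms are then compared on this change by generalized linear modelling. For the secondary outcomes, which include steroid bursts, hospitalisations, emergency visits and unscheduled physician visits, it says: "A similar analytic approach will be used for other clinical and inflammation outcomes". The same sentence allows tests and models that fit the type of data. Its examples, chi-square and logistic regression, are for dichotomous outcomes.

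The primary analysis dataset is limited to children with six-month outcome data. Models over several visits are named only for the *S. aureus* aim. Potential confounders include baseline treatment step, allergen and pollutant levels, and season. Baseline severity, control and lung function are listed as potential effect modifiers. Nothing commits the plan to adjusting each secondary outcome for its own baseline.

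Health care utilisation questionnaires are given at every clinic visit, with no recall window stated. The only burst windows in the document are in the control-level tables: "Steroid bursts, previous six months" at screening (Table 2) and "Steroid bursts, since last visit" at CV1–CV4 (Table 2a, recorded as NO/YES). Clinic visits after randomisation are two months apart.

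**The concern.** The one approach described is a difference between two visits. That is reasonable for a treatment step, which exists at each visit. It does not carry over naturally to events that accumulate. Applied literally with the only burst windows available, it would set about two months of follow-up against six months of history, leave four of the six post-randomisation months unused, and give a difference on no interpretable scale. A child who leaves after CV3 would contribute no events.

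The sentence on suitable models leaves a better analysis open but does not choose it. Window, scale and model could therefore be settled after the data are seen, in a trial whose families are not blinded. For FENO, lung function, CASI and symptom days there is no window problem. There the issue is efficiency: a change score is less precise than adjustment for baseline, and the CV2 and CV3 measurements have no stated role.

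**Working it through.** **The plan's own figure.** Section 6c gives power only for the primary outcome. It "estimated the power to detect a difference of 1 treatment step between the two groups" and reports: "With a sample size of 200, and assuming alpha=0.05, we will have a power of 0.94 to detect a difference of this magnitude". With n per arm, power ≈ Φ(δ/σ·√(n/2) − 1.96). For δ = 1, σ = 2, n = 100: 0.5 × √50 = 3.54, and Φ(1.58) = 0.94. For 87.5 per arm: 0.5 × √43.75 = 3.31, and Φ(1.35) = 0.91, against the stated 0.90. All eight cells of Table 6 reproduce within 2 points. No power is stated for exacerbations.

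**Inputs for exacerbations.** From the document: 1:1 allocation, 200 children, about 12% drop-out (200 × 0.88 / 2 = 88 per arm), visits every two months, and CV1 about 1.5 months after screening. Assumed, because the document gives none: control rate 0.3, 0.6 or 1.0 events per six months; rate ratio 0.5 or 0.7; gamma dispersion k of 0.5 or 1.0; pre-study rate 1.5 times the on-study control rate.

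**Worked example:** control rate 0.6, rate ratio 0.5, k = 1, immediate effect. Gamma-Poisson counts with means m₁ and m₂ in the same child give Var(count₁ − count₂) = m₁ + m₂ + k(m₁ − m₂)².

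- (a) CV4 two-month count minus screening six-month count. Control means 0.2 and 0.9, variance 1.1 + 0.49 = 1.59. ECS means 0.1 and 0.9, variance 1.0 + 0.64 = 1.64. SE = √(3.23/88) = 0.192, z = 0.1/0.192 = 0.52.
- (b) CV4 minus the 1.5-month CV1 count, run-in at the on-study rate (mean 0.15). Variances 0.3525 and 0.2525. SE = √(0.605/88) = 0.083, z = 1.21.
- (c) Six-month total minus six-month history. Variances 1.5 + 0.09 = 1.59 and 1.2 + 0.36 = 1.56. SE = √(3.15/88) = 0.189, z = 0.3/0.189 = 1.59.
- (d) All events CV1–CV4, log rate ratio. Variance = (1/0.6 + 1 + 1/0.3 + 1)/88 = 7.0/88, SE = 0.282, z = 0.693/0.282 = 2.46.

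| Analysis | Power, formula | Power, simulation (2,000 trials) |
|---|---|---|
| (a) | 0.08 | 0.08 |
| (b) | 0.23 | 0.22 |
| (c) | 0.35 | 0.34 |
| (d) | 0.69 | 0.71 |

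**Over the whole assumed range (simulation):**

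| | Immediate effect | No effect in months 0–2 |
|---|---|---|
| (d) power, all events | 0.19–0.91 | 0.10–0.54 |
| (a) power | 0.06–0.11 | 0.05–0.11 |
| (a) relative loss against (d) | 68–90% | 50–80% |
| (b) relative loss against (d) | 57–74% | 12–45% |

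For (c), the relative loss with an immediate effect is 37–56%. With no true effect, every test rejected in 4–6% of trials.

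**With baseline adjustment.** A separate simulation (rate ratio 0.6, dispersion 0.8, rates 0.5 and 0.8 per six months, immediate effect) gave 0.08 and 0.10 for (a), 0.20 and 0.30 for a count model on CV4 alone, and 0.47 and 0.67 for all events adjusted for the baseline count.

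**Continuous outcomes.** With equal variance at both visits and correlation r, the relative variance is 2(1 − r) for a change score and 1 − r² with baseline as covariate. At r = 0.5 these are 1.00 and 0.75, a 25% reduction. The correlation is an assumption.

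**The case against.** The strongest reply is that the plan does not state the flawed analysis. The subtraction sentence names only the treatment step, the extension to other outcomes allows models that suit the data, and generalized linear models include count models. The burst windows come from tables that drive treatment, not from an endpoint definition. Table 2a is NO/YES, so a count minus that entry can hardly be the planned endpoint, and no window at all is given for the other three event types. All of this stands. It changes the finding from a wrong analysis to an unspecified one.

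The size also depends on the reading. CV1 is a natural baseline, and its look-back is close to the two months at CV4. Section 6c itself expects the effect to take months. With no effect in months 0–2, a plain CV4 count does about as well as the six-month total (0.35 against 0.32 in the example), so the harm then comes from subtracting history rather than from leaving out CV2 and CV3. Even all events often give modest power. Bursts also depend partly on families, who hold a home course, and on physician discretion, so they are not a fully objective outcome.

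For continuous outcomes, adjusting a change score for its own baseline gives the same treatment effect as ANCOVA, and the planned regression models could do this. The plan does not commit to it. Month 6 was chosen for a stated reason, and the fix keeps it.

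**Conclusion.** The point holds as an under-specified secondary analysis with a nearly free improvement. The plan gives no window, count model or CV2–CV3 rule for exacerbations, and the one approach it describes would serve them poorly.

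A reader might infer that exacerbation counts will be subtracted over unequal windows, that CV2 and CV3 events will be ignored, and that most of the power will be lost. The document states neither of the first two. The third holds for the literal CV4-minus-screening change, where at least half the power is lost in every scenario tried. It does not hold in general: the loss is 12–45% with a CV1 baseline and a lag, and 37–56% with equal six-month windows and an immediate effect.

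Every exacerbation power figure rests on assumed rates, rate ratios and dispersion. The windows are the same in both arms, so the matter is precision and interpretability, not type I error. The primary outcome and Table 6 are untouched. The window issue does not extend to FENO, lung function or the two-week symptom items. If the primary dataset rule also governs secondary outcomes, about 24 of 200 children (12%) could be excluded from them.

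**What to change.** Add to section 6c:

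1. Each exacerbation outcome is the number of events reported from randomisation (CV1) to CV4. Arms are compared by negative binomial regression with log follow-up time as offset and baseline history as covariate, including all randomised children with any follow-up. If an event type is recorded only as YES/NO per interval, use the number of intervals with an event, or any event.
2. FENO, lung function, CASI and symptom days are analysed in a repeated-measures model of CV2, CV3 and CV4, with the outcome's own baseline as covariate instead of a change score and with arm-by-visit terms. The month-6 contrast is the reported effect.
3. Allergen-specific IgE, for which blood is drawn only at screening and CV4, is analysed by ANCOVA on its screening value.

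State also which visit is the baseline for each outcome, and the recall window of the utilisation questions. The visit schedule already covers these assessments, so the change is wording only. The one point to confirm is whether burst counts or only YES/NO are recorded. The downside is slightly more modelling work.
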